7.1.5 SAE/AE occurring only with general anesthesia

- Malignant hyperthermia: some patients can have a severe reaction to general anesthesia that includes a substantial increase in body temperature (sometimes as

high as 113° F) and rigid/painful muscles. If this occurs during surgery, the operation will immediately be stopped and patients will receive intravenous dantrolene. Patients will be admitted to the intensive care unit where they will continue to receive care including cooling blankets and fluids, oxygen, correction of electrolyte abnormalities, and standard medications to manage tachycardia and hypotension. We will also monitor kidney function and changes in creatinine kinase. The occurrence of this complication will not change the study intervention regimen or the schedule of participant assessments.

- Urinary retention: per our standard hospital protocol, if patients are unable to urinate by four hours after surgery, we will perform a bladder scan. If >200 mL of urine is seen, the patient will receive an in-and-out catheterization followed by observation for up to an additional four hours. If the patient is still unable to urinate, they will have a Foley catheter placed, be admitted for overnight observation, and be evaluated by urology. Typically, the patient goes home with a Foley leg bag and undergoes urodynamic testing 1 to 2 weeks later after being discharged with medication for benign prostatic hypertrophy. The occurrence of urinary retention will not change the study intervention regimen or the schedule of participant assessments.

7.2 Methods and Timing for Assessing, Recording, and Analyzing Safety Parameters

7.2.1 Assessing and recording

At each study visit, research assistants will actively elicit evidence of SAE and AE by asking questions related to symptoms and conducting physical exam in conjunction with the clinical team (which should be examining for these complications as well up to the 2 week postoperative time point). For the 6 month visit, symptoms will be elicited by asking questions via phone. At each time point, after reviewing the list of SAE and UE, an open-ended question will be asked regarding whether the patient is having any other additional problems or concerns. Any SAE/AE will be conveyed to the clinical team if not already identified, documented in the research record, and referred to the data safety and monitoring board immediately upon ascertainment.

Information to be collected includes event description, time of onset, severity, relationship to study arm, and time of resolution/stabilization. All AE occurring during the study will be documented regardless of relationship to study assignment and all will be followed to adequate resolution

Any medical condition present at the time of screening will be considered as patient baseline and will not be reported as an AE. If the condition deteriorates during the study, it will be recorded as an AE. UP will be recorded in the research record throughout the study. Changes in severity of an AE will be recorded to allow an assessment of duration at each level of severity to be performed. AE found to be intermittent will have documentation of each episode onset and duration. We will record all events with start dates occurring after informed consent until 30 days after the last date of study participation.

7.2.2 Classification of AE

7.2.2.1 Severity

For AE not included in the protocol defined grading system, the following guidelines will be used to describe severity:

- Mild: requires minimal/no treatment and do not interfere with participant's daily activities
- Moderate: low level of inconvenience or concern with the therapeutic measures. May cause some interference with functioning.
- Severe: interrupt a participant's usual daily activity and may require systemic therapy or other treatment. Usually potentially life-threatening or incapacitating.

Other AE will be graded according to Common Terminology Criteria for Adverse Events version 5.0 severity.¹⁷

7.2.3 Relationship to study assignment

For all collected AE, the causality will be determined by the temporal relationship and clinical judgement of the assessor. The degree of certainty about causality will be graded as follows:

- Definitely Related – There is clear evidence to suggest a causal relationship, and other possible contributing factors can be ruled out. The clinical event, including an abnormal laboratory test result, occurs in a plausible time relationship to drug administration and cannot be explained by concurrent disease or other drugs or chemicals. The response to withdrawal of the drug (dechallenge) should be clinically plausible. The event must be pharmacologically or phenomenologically definitive, with use of a satisfactory rechallenge procedure if necessary.
- Probably Related – There is evidence to suggest a causal relationship, and the influence of other factors is unlikely. The clinical event, including an abnormal laboratory test result, occurs within a reasonable time after administration of the drug, is unlikely to be attributed to concurrent disease or other drugs or chemicals, and follows a clinically reasonable response on withdrawal (dechallenge). Rechallenge information is not required to fulfill this definition.
- Possibly Related – There is some evidence to suggest a causal relationship (e.g., the event occurred within a reasonable time after administration of the trial medication). However, other factors may have contributed to the event (e.g., the participant's clinical condition, other concomitant events). Although an AE may rate only as "possibly related" soon after discovery, it can be flagged as requiring more information and later be upgraded to "probably related" or "definitely related," as appropriate.
- Unlikely to be related – A clinical event, including an abnormal laboratory test result, whose temporal relationship to drug administration makes a causal relationship improbable (e.g., the event did not occur within a reasonable time after administration of the trial medication) and in which other drugs or chemicals or underlying disease provides plausible explanations (e.g., the participant's clinical condition, other concomitant treatments).
- Not Related – The AE is completely independent of study drug administration, and/or evidence exists that the event is definitely related to another etiology. There must be an

alternative, definitive etiology documented by the clinician

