- Quality of life: we will use the 8-item Carolinas Comfort Scale to assess hernia-related quality of life
- Presence of symptoms indicating urinary retention (if not already identified by clinical team during history and physical)

For participants who have successfully been screened for eligibility and are enrolled into the study, baseline assessments are performed against which to measure the study outcome. They also ensure that the groups are balanced with respect to baseline characteristics. For example if the study hypothesis is “dietary intervention and exercise will reduce body weight by X% within one year”, body weight will be assessed and documented.

List and briefly describe all baseline evaluations in a bulleted format.

Randomization

As outlined in section 4.4, randomization will occur immediately after screening and baseline assessment because the anesthesia team will need to be aware of the anesthetic plan prior to surgery, and the anesthesia team sees patients in their clinic after the surgical visit is complete. The study intervention (use of local or general anesthesia) will occur at the time of surgery, typically 4-6 weeks after the surgical clinic visit occurs and randomization is completed.

Randomization must precede intervention administration in a randomization study. Specify time window for (a) randomization relative to completion of screening and baseline and (b) initiation of study intervention relative to randomization.

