8 INTERVENTION DISCONTINUATION

The study will be halted if three grade 3 AEs are identified and determined to be probably related or definitely related to the study interventions (distinct from surgical complications). The PI will notify NIA and the IRB immediately when the third grade 3 event is reported, and enrollment screens will stop accepting new study participants.

Participants may voluntarily withdraw/stop participation at any time and for any reason (noted on consent form). If participants withdraw, we will make every effort to obtain permission and convince them to complete planned evaluations and will try counseling patients to re-enroll in the study if possible. We will also make every effort to continue monitoring and treating AE/SAE for participants who withdraw.

There will be no replacement of participants who withdraw early. Additionally, we will continue to follow participants, with their permission, even if the study intervention is discontinued.

List criteria for discontinuing the study intervention/product (e.g., development of toxicities, study closure by institute) for a participant and methods for determining when criteria are met.

If relevant, include criteria for temporary discontinuation of treatment and define its length.

Also note that subjects may withdraw voluntarily from participation in the study at any time and for any reason. Participants should continue to be followed, with their permission, even if the study intervention is discontinued. Discuss any modifications to the schedule and duration of continued follow-up and indicate the evaluations to be completed while the participant is either temporarily or permanently discontinued from study intervention but followed for outcomes, if applicable.

This section should also include a discussion of replacement of subjects who discontinue early, if replacement is allowed.

Note: It is vital to collect safety data on any subject discontinued due to an AE or SAE. In any case, every effort must be made to undertake protocol-specified safety follow-up procedures. If voluntary withdrawal occurs, the subject should be asked to continue scheduled evaluations, complete an end-of-study evaluation, and be given appropriate care under medical supervision until the symptoms of any AE resolve or the subject's condition becomes stable.

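### The causality definitions in 7.2.3 rely on drug withdrawal, which fits a one-time anesthetic poorly, and Section 8 names only grade 3, so the gravest anesthesia-related events may not count toward the halt

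*Combined protocol and SAP*

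**What the plan says.** Four parts of the combined protocol and SAP bear on this point.

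- **7.2.3 (relatedness).** Probably Related joins three criteria: reasonable timing, another cause being unlikely, "and follows a clinically reasonable response on withdrawal (dechallenge". Its next sentence waives rechallenge only. Definitely Related says: "The response to withdrawal of the drug (dechallenge) should be clinically plausible". It also wants other contributing factors ruled out, and mentions rechallenge where necessary. The section opens by stating that "the causality will be determined by the temporal relationship and clinical judgement of the assessor", and says of a Possibly Related event that "it can be flagged as requiring more information and later be upgraded".
- **6.2.2 (exposure).** "The study intervention (use of local or general anesthesia) will occur at the time of surgery". There is one exposure per patient.
- **8 (halt).** "The study will be halted if three grade 3 AEs are identified and determined to be probably related or definitely related to the study interventions". Surgical complications are set apart. The second sentence of the rule again refers to grade 3 only.
- **7.2.2.1 (severity).** One scale has three unnumbered levels (mild, moderate, severe). Its top level is described as "Usually potentially life-threatening or incapacitating". Other events go to CTCAE version 5.0, whose grades are not printed in the document.

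Section 9.3 gives a different trigger: a temporary halt to enrollment once three AEs occur, with no grade or relatedness condition and no formal stopping rules.

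**The concern.** A response to withdrawal is informative when a drug is given over time and can be stopped. After a single anesthetic, nothing remains to be stopped at the pre-discharge, 48-hour, two-week and six-month assessments. Section 2.2 names venous thromboembolism, heart attack, stroke and cognitive dysfunction among the risks of general anesthesia. When such an event appears or persists after surgery, an assessor who follows the Probably Related definition closely has no withdrawal response to record and may settle on Possibly Related. Section 8 does not count that category.

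The grade wording adds a second gap. Read literally, an event graded above 3 is not a grade 3 event. An event rated on the three-level scale has no number, and that scale has no separate level for death.

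At stake is the only halt rule in the protocol that states both a grade and a relatedness condition. Whether it responds to the most serious harms would depend on how each assessor reads it.

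**Working it through.** The plan gives no operating characteristic for the halt rule, so there is no figure to reproduce. The check is first a reading of the text, then an illustration.

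**Step 1: which events pass both conditions in Section 8?**

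| Event type | Withdrawal criterion (7.2.3) | Grade condition (8) |
|---|---|---|
| Acute reaction during surgery (7.1.4 and 7.1.5 have the operation cancelled or stopped) | Can be assessed | Counts if graded 3 |
| Stroke, infarction, lasting cognitive decline, appearing or persisting later | No recovery on withdrawal to observe; depends on the assessor | Counts if graded 3; unclear if rated only Severe |
| Death | Same | No separate level on the three-level scale; not named in Section 8 |
| Any event graded above 3 | Depends on the event | Not named in Section 8 |

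Of the two qualifying categories, Probably Related is the more reachable for a late event. Definitely Related is softer on withdrawal but requires other factors to be ruled out, which is hard for a vascular event after surgery in patients aged 65 or over.

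**Step 2: how much does the share of events that count matter?**

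Inputs:
- n = 80 patients (9.2.1).
- Three events trigger the halt (Section 8), which is 3/80 = 3.75% of patients.
- p = true rate of severe anesthesia-related events. This is assumed, from 1% to 10%. Section 7.5 gives a risk below 1%, but the event label there is truncated.
- s = share of those events that the relatedness and grade wording lets count. This is assumed.

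With at most one event per patient and independence between patients, put q = p × s. Then

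P(at least 3) = 1 − Σ (k = 0 to 2) C(80, k) q^k (1 − q)^(80 − k).

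For p = 5% and s = 1, q = 0.05. The terms for k = 0, 1, 2 are about 0.017, 0.070 and 0.145, so P is about 0.769.

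| p | all count (s = 1) | half count (s = 0.5) | none count (s = 0) |
|---|---|---|---|
| 1% | 4.7% | 0.8% | 0 |
| 2% | 21.6% | 4.7% | 0 |
| 5% | 76.9% | 32.3% | 0 |
| 10% | 98.9% | 76.9% | 0 |

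If a quarter count at p = 5%, the probability is 7.9%. If the events arise only among the 40 general-anesthesia patients, the p = 5% row becomes 32.3%, 7.8% and 0.

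Only the product p × s matters: halving the share that counts has the same effect as halving the true event rate. The column for s = 0 is a limit, and the text does not establish it.

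**The case against.** A reader might infer that the worst harms can never trigger the halt, that assessors must rate them no higher than Possibly Related, and that no other trigger exists. The documents do not support any of these.

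- **Judgement and upgrade.** Section 7.2.3 bases causality on timing and clinical judgement and allows later upgrading. Definitely Related asks only for plausibility, and a flexible assessor could accept a persisting stroke as a plausible course. This stands against any claim of impossibility. It does not remove the gap: judgement is exercised through the listed definitions, and an upgraded event must still fit one of the same two categories.
- **An anesthetic can be withdrawn.** It can, during surgery. The protocol foresees this for allergic reactions and malignant hyperthermia, so acute reversible reactions can qualify.
- **Other limits may bind first.** Section 8 excludes surgical complications, and 7.5 attributes most complications to surgery. Late vascular events might stay at Possibly Related even without the withdrawal clause. This stands, and it means that rewording alone may not make every such event count.
- **Severe may be what grade 3 means.** It is the third of three levels and covers life-threatening events. If that mapping is intended, such events count. The protocol does not state it, so the grade gap is an ambiguity and not a proven exclusion.
- **Other safeguards exist.** They include the three-AE pause in 9.3, immediate referral of AEs and SAEs to the DSMB (7.2.1), SAE reports to the IRB and NIA within 24 hours (7.3.2), and discontinuation by oversight bodies (11.4). Three deaths recorded as AEs would meet the 9.3 pause. These routes limit the consequence, but they do not say what Section 8 counts, and 9.3 refers back to a rule whose conditions differ from its own.

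**Conclusion.** The point holds as a misfit in stated rules. The withdrawal criterion does not suit a single exposure, and Section 8 does not say how it treats events above grade 3, deaths, or events whose response to withdrawal cannot be assessed. Such events may therefore go uncounted.

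The size depends on two quantities that the documents do not fix: the true event rate and the share that assessors would count. If the rate is at or below 1%, the halt would be reached in at most about 4.7% of such trials even with every event counted, so the practical effect is small. The gap matters if the rate proves higher than expected, which is the situation a halt rule exists for: at 5%, counting half the events instead of all lowers the chance of a halt from 76.9% to 32.3%. These figures assume independent patients with at most one event each, and they describe Section 8 alone, without the pause in 9.3.

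**What to change.** 1. **7.2.3:** remove the withdrawal and rechallenge clauses. Define Probably Related and Definitely Related for a single exposure by plausible timing after the anesthetic, a recognised effect of that type of anesthetic, and no more likely surgical or disease cause.
2. **7.2.2:** use one numbered severity scale for all AEs, or print a mapping of every level, including death, to the numbers used in Section 8.
3. **8 and 9.3:** reconcile the two triggers with each other and with 7.2.2 and 7.2.3. State explicitly how events above grade 3, deaths, and events with no assessable withdrawal response are counted, and make both sentences of the Section 8 rule agree. The threshold itself is for the sponsor and the DSMB to set.
4. Re-rate any event already classified under the present wording.

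The cost is wording changes and IRB review of the amendment. Severity and relationship are already recorded for each event (7.2.1), so no new data item or change of sample size is needed. The downside is that a pause becomes somewhat more likely: for example 4.7% instead of 0.8% at a 1% event rate, if half the events would otherwise have gone uncounted and all are counted after the change.

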7.3 Reporting Procedures

7.3.1 Adverse event reporting procedures

All AE will be reported to the IRB and NIA regularly and within 30 days of occurrence

7.3.2 Serious adverse event reporting procedures

Any occurrence that meets a protocol-defined SAE criterion will be submitted immediately (within 24 hours of identification) on an SAE form to the IRB and NIA. The principal investigators monitor will review and assess the SAE for regulatory reporting and potential impact on study subject safety and protocol conduct.

At any time after completion of the study, if the investigator becomes aware of an SAE that is suspected to be related to study product, the investigator will report the event to the IRB and NIA.

All clinical trials must have a safety reporting system in place. Include details of the reporting procedures and time lines, including the individual responsible for each step (e.g., the Investigator, the Medical Monitor, etc.), how decisions will be made regarding determining relatedness and severity, which forms should be completed, (specific information on where to send this form is included), how reports will be distributed and what follow-up is required.

7.3.3 Unexpected event reporting procedures

All unanticipated problems will be reported to the IRB within five days of receiving notice of the event if the event requires immediate intervention to prevent serious harm to participants or others. All other unanticipated problems will be reported to the IRB as soon as possible and no later than ten business days from the date of the event or from the date the investigator is notified of the event.

Investigators will promptly report (according to the above schedule) the following events to the IRB if the events occur within 30 days of participants' active participation:

- Adverse events which in the opinion of the principal investigator are both unexpected and related to the study interventions.
- An unanticipated event related to the research that exposes individuals other than the research participants (e.g., investigators, research assistants, public, etc.) to potential risk
- Information that indicates a change to the risks or potential benefits of the research.
- An interim analysis or safety monitoring report indicates that frequency or magnitude of harms or benefits may be different than initially presented to the IRB.
- A paper is published from another study that shows that the risks or potential

benefits of your research may be different than initially presented to the IRB.

- A breach of confidentiality.
- Incarceration of a participant in a protocol not approved to enroll prisoners.
- Change to the protocol taken without prior IRB review to eliminate an apparent immediate hazard to a research participant.
- Complaint of a participant when the complaint indicates unexpected risks or cannot be resolved by the research team.
- Protocol violation (accidental or unintentional change to the IRB approved protocol) that harmed participants or others or that indicates participants or others may be at increased risk of harm.
- Any other event that indicates participant or others might be at risk of serious, unanticipated harms that are reasonably related to the research.

7.4 Follow-up for Adverse Events

AEs will be followed until resolution even if this extends beyond the study-reporting period. Resolution of an AE is defined as the return to pretreatment status or stabilization of the condition with the expectation that it will remain chronic.

Describe how AEs will be followed until resolved or considered stable. Specify duration of follow-up.

7.5 Safety Monitoring

The NIA Guidelines on Data and Safety Monitoring generally require that a NIA-appointed Data and Safety Monitoring Board or Safety Officer monitor clinical trials. Please see the Safety Monitoring Guidelines (a link will be inserted here).

Inguinal hernia repair is generally considered a safe procedure with very few (<1% risk of E).^{3,7,8} Both local and general anesthesia are considered reasonable standard of care for the operation, and there are generally few AE or SAE resulting directly from the anesthesia modality. Most complications, AE, SAE, or UP result from the surgery rather than anesthesia, and the surgical technique is the same for both study arms. Consequently, we will convene our data safety and monitoring board to review all AE, SAE, and UP once 50% of expected enrollment is obtained. The UT Southwestern Department of Surgery maintains a standing DSMB for monitoring of all trials in our department. Given that all published studies of local versus general anesthesia have been completed without significant rates of adverse events or early termination, it is highly unlikely that the use of stopping rules will be required.

